**Detectable Effect Size**

To account for the anticipated dilution of treatment effect due to 8% of the subjects being noncompliant with treatment, dropping out of the study or experiencing an unanticipated delay of surgery beyond 21 days, the sample size estimate is inflated to 39 subjects in total (26 subjects on the ACTOplus met® XR arm and 13 subjects on the placebo arm). Because of a short duration of treatment, we do not expect any random loss to follow-up.

The anticipated accrual rate is 1-2 subjects/month; therefore, our planned enrollment of 39 subjects should occur over 12-18 months.

Protocol accrual will be monitored through the NCI Division of Cancer Prevention's Accrual Quality Improvement Program (AQuIP). DCP will create an Accrual Zone Monitoring Plan for this protocol with milestones established based on the target enrollment, the projected monthly accrual rate and the projected duration of accrual. The CLO will submit accrual reports monthly to the Division of Cancer Prevention. If accrual falls below 90% of the projected goal, a corrective action plan will be required to ensure full enrollment within the stated accrual period. If accrual falls below 75% of the projected goal, an analysis of recruitment barriers and corrective recruitment action plan will be required. If accrual is falling short of the projected goal by > 75%, i.e. below 25% of the projected goal, at the quarter or half way marks, study continuation will require approval by DCP leadership.

For information regarding the study population (including gender and minority considerations), please see Section 4.3 Inclusion of Women and Minorities.

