### 3. SUMMARY OF STUDY PLAN

This is a 2:1 randomized, placebo-controlled, phase IIB oral cavity/oropharynx window of opportunity cancer chemoprevention study of ACTOplus met® XR (pioglitazone 30 mg and metformin extended release 1000 mg) daily for 10-21 days in patients undergoing planned surgery or definitive radio/chemotherapy. We plan to accrue 36 evaluable participants to this protocol. To account for an anticipated dropout rate of 8%, 39 participants will be accrued over a 12-18-month period of time. This number allows for three (3) unevaluable participants. (Note: this will start as a pilot study of the first 18 participants accrued to the protocol). Assuming a screening rate of approximately 2 participants per month and an accrual rate of 1-2 participants per month (0.5-1 per site), we expect the study to be complete within 18–24 months.

Study recruitment will occur in head and neck cancer clinics at participating institutions. Surgeons will be critical to recruitment as patients with newly diagnosed head and neck cancer will usually first meet with a surgeon.

Candidates for this protocol will be patients with newly diagnosed, histologically confirmed, stage I-IV squamous cell carcinoma or squamous cell carcinoma in situ of the oral cavity or oropharynx who will be undergoing definitive treatment (surgical, radiotherapy, chemoradiation treatment). Patients with a lesion in the oral cavity or oropharynx that is not yet biopsied, but is highly suspicious for squamous cell carcinoma, are candidates for screening but will not be randomized if the diagnosis is not pathologically confirmed. Study candidates must have a primary tumor and adjacent visually normal appearing tissue in an area that would allow for the collection of a 4 mm tissue sample from each for biomarker analysis at baseline and at the end of study.

Informed consent will be obtained prior to performance of any study procedures. The following assessments will be completed within 30 days prior to day 1 of study agent dosing. If any of these tests were conducted as part of the participant's standard medical care within the required 30 day time frame and a copy of the source document can be obtained for the study chart, those tests do not need to be repeated. If the testing is incomplete [i.e. some, but not all of the required blood tests were obtained or a

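### Accruing 39 participants at the stated 1-2 per month takes 19.5 to 39 months, so the 12-18 months in sections 3 and 13.3 does not follow

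*Combined protocol and SAP*

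**What the plan says.** Section 13.3 (Accrual and Feasibility) inflates the target from 36 to 39 participants, 26 active and 13 placebo. In the text after the table of detectable effect sizes it then draws the timeline: "The anticipated accrual rate is 1-2 subjects/month; therefore, our planned enrollment of 39 subjects should occur over 12-18 months".

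Section 3 (Summary of Study Plan) gives the same duration for the same number: "39 participants will be accrued over a 12-18-month period of time". It puts screening at about 2 participants per month and continues with "an accrual rate of 1-2 participants per month (0.5-1 per site), we expect the study to be complete within 18–24 months".

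Section 13.3 also says how these figures will be used. The sponsor will create an accrual monitoring plan "with milestones established based on the target enrollment, the projected monthly accrual rate and the projected duration of accrual". If accrual falls below 90% of the projected goal, "a corrective action plan will be required to ensure full enrollment within the stated accrual period". Below 75%, an analysis of recruitment barriers and a corrective recruitment plan are required. Below 25% at the quarter or half-way mark, continuation needs approval from the sponsor's leadership.

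**The concern.** Section 13.3 presents the duration as a consequence of the rate, yet the fastest stated rate overruns the longest stated duration. Target, rate and duration therefore cannot all be right.

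The three figures are also the named inputs to the accrual milestones, and the corrective-plan clause refers back to the stated accrual period. If the milestones are built on 12-18 months, a trial recruiting as projected could be classed as under-recruiting and asked for plans to meet a date that its own rate cannot reach. What is at stake is timeline and oversight, not inference.

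**Working it through.** **Inputs**

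- Target N = 39 (sections 3 and 13.3); evaluable target 36 (sections 3 and 13.3).
- Accrual rate r = 1-2 per month (both sections), equal to 0.5-1 per site (section 3).
- Screening rate of about 2 per month (section 3).
- Stated accrual duration T = 12-18 months (both sections).
- Stated time to study completion 18-24 months (section 3).

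**Attempt to reproduce the stated 12-18 months.** Duration = N / r.

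| Rate per month | N = 39 | N = 36 |
|---|---|---|
| 1 | 39 months | 36 months |
| 1.5 | 26 months | 24 months |
| 2 | 19.5 months | 18 months |

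The stated range is not reproduced. Replacing 39 by 36 recovers only the 18-month end, and only at the top rate. The 12-month end is not reached at any stated rate.

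**Per-site reading.** If 1-2 were a rate per site with two sites, the total would be 2-4 per month and the duration 39/4 = 9.75 to 39/2 = 19.5 months. Section 3 excludes this: it equates 1-2 per month with 0.5-1 per site (1/0.5 = 2/1 = 2 sites implied), so 1-2 is the total.

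**Reverse check.** Rate needed = N / T.

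- 18 months: 39/18 = 2.17 per month.
- 12 months: 39/12 = 3.25 per month.

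Both exceed the maximum stated accrual rate and the stated screening rate. Accrual of 2 per month from about 2 screened per month already leaves no room for screen failures, which sections 3 and 4.1 expect.

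**Number accrued in the stated time.** Twelve months at 1-2 per month gives 12-24 participants; 18 months gives 18-36. The best case is 3 short of 39.

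**Completion in 18-24 months.** Accruing 39 by month 24 needs 39/24 = 1.63 per month. Allowing 26 days (0.85 month) on study for the last participant, 39/(24 - 0.85) = 1.68, or about 1.7 per month. At 2 per month the last participant would finish at about 19.5 + 0.85 = 20.4 months. So this figure fits the upper part of the stated rate range, taking completion as the end of the last participant's dosing window and assuming no gap between accrual and first dose.

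**Effect on the triggers.** The monitoring plan is not in the documents. Assume linear milestones reaching 39 at the end of the stated period; percentage of goal = r / (39/T).

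| | 18-month plan | 12-month plan |
|---|---|---|
| 1 per month | 46% | 31% |
| 1.5 per month | 69% | 46% |
| 2 per month | 92% | 62% |
| 90% trigger fires below | 0.90 × 2.167 = 1.95 per month | 0.90 × 3.25 = 2.93 per month |
| 75% trigger fires below | 0.75 × 2.167 = 1.63 per month | 0.75 × 3.25 = 2.44 per month |
| 25% trigger fires below | 0.25 × 2.167 = 0.54 per month | 0.25 × 3.25 = 0.81 per month |

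On a 12-month plan the 90% and 75% triggers fire at every stated rate. On an 18-month plan, only rates of at least 1.95 per month avoid both. The 25% trigger is not reached at any stated rate on either plan.

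**The case against.** The division cannot be disputed, but four points limit what follows from it.

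- **The documents do not show which figure is wrong.** The duration may be as intended and the rate too low. The implied two sites are an inference from the per-site figure. This stands: 19.5 to 39 months is conditional on the stated rate, and the correction must allow either figure to change.
- **The consequence is hypothetical.** The monitoring plan has yet to be created and will use all three inputs. Milestones following 1-2 per month would not penalise accrual at the projected pace, and whoever sets them may notice the conflict. This also stands. The trigger percentages depend on the linear assumption, and the result that two triggers fire at every rate belongs to the 12-month plan alone.
- **The 18-month end is nearly met.** At 2 per month the shortfall is 3 of 39, and the 90% trigger does not fire even on a linear plan. If accrual were Poisson with mean 36 over 18 months (an assumption), the chance of reaching 39 would be about 0.33. This helps one corner of the range only; at the same rate over 12 months (mean 24) the chance is about 0.003.
- **The completion figures are best case.** Section 3 does not define completion. Section 10 places the final slide request and the RNA shipment after the last participant finishes, and dosing may start some time after randomisation. If assays count, a rate above 1.7 per month would be needed. This is a side point and leaves the main inconsistency untouched.

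**Conclusion.** The concern holds, as a minor arithmetic error. From the plan's own target and study-wide rate, accrual takes 19.5 to 39 months (26 at 1.5 per month), against 12-18 months stated in two sections. The stated duration would need 2.17-3.25 participants per month. No stated combination of rate and duration reaches 39.

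This conclusion needs only division and the study-wide reading that section 3 supplies. The effect on the accrual triggers rests further on linear milestones tied to the stated duration, which the documents neither confirm nor exclude. Nothing here changes the sample size, the power or the primary comparison of Ki-67 change.

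**What to change.** State one consistent rate and duration in sections 3 and 13.3. The sponsor can do either of the following:

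- keep 1-2 per month and give the accrual period as about 20-39 months (26 at 1.5 per month); or
- keep 12-18 months and commit to 2.17-3.25 participants accrued per month, with a screening rate high enough to supply them after screen failures.

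Align the 18-24 month completion figure with the chosen pair and say what completion means. If it means the end of the last participant's dosing window, the figure needs about 1.7 per month or more. Use the corrected pair as the input when the accrual monitoring plan is drawn up.

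The cost is wording in two sections. The downside is a longer, less favourable stated accrual period, or a commitment to recruit and screen faster.

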#### 13.4 Primary Objective, Endpoint(s), Analysis Plan:

The primary objective of this protocol is to determine whether 10-21 days of treatment with ACTOplus met® XR will result in a decrease in proliferation index (Ki-67) expression in oral cavity/oropharyngeal tumor tissue in the aerodigestive tract as compared to placebo. The primary endpoint of the study is the absolute change in proliferation index (Ki67) expression in oral cavity cancer cells from baseline to post-exposure. Baseline, post-exposure, absolute change in Ki-67, and difference in absolute change between the ACTOplus met® XR and placebo subjects will all be summarized with descriptive statistics. The primary analysis will compare the difference in absolute change in Ki-67 between the ACTOplus met® XR and placebo arms using a two-sided two-sample Student's t-test or Wilcoxon rank-sum test, as appropriate, at a significance level of 0.05.

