#### 6.8.2 Randomization:

Participants who meet the eligibility criteria for the protocol will be randomized by the CLO. The PO will request randomization of a study participant by submitting (via fax or e-mail) the following documents to the CLO:

Informed Consent Form  
Eligibility Questionnaire  
Clinical safety/Eligibility lab report  
Pre-study diagnostic biopsy report  
Medical/Surgical History Worksheet

(Note: all documents submitted to the CLO must have personally identifying information deleted or completely obscured and be re-identified with the participant's PID number. Documents with visible personally identifying information will not be accepted.)

A CLO coordinator will review these documents and confirm that the participant meets the eligibility criteria and that the correct version of the ICF was signed. If eligibility is confirmed, the CLO coordinator will assign the next randomization (bottle) number in sequence for that site from a randomization list that will be pre-generated by the Statistical Center at UWCCC, as described in Section 6.4. The CLO will notify the site of the randomization number assigned to the participant. This number will correspond to the randomization number of one of the bottles of study agent issued to the site. That bottle will be requested from the site's pharmacy or other entity delegated the responsibility of study agent accountability following the site's institutional policy for requesting and dispensing study agent.

**Study agent should not be started within 48 hours following administration of an iodinated contrast agent** (commonly used in a staging CT scan). The participant's eGFR must be assessed  $\geq 48$  hours after the scan and the result must be within normal limits (see section 5.4.5) before starting study agent. To avoid missing doses of study agent (which could potentially render the participant unevaluable) if a staging test using iodinated contrast agent is planned, do not start the participant on study agent until the scan has been completed and their  $\geq 48$  hour post scan eGFR is confirmed to be within normal limits.

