### **13. STATISTICAL CONSIDERATIONS**

#### **13.1 Study Design/Description:**

This is a randomized, placebo-controlled, phase IIB oral cavity/oropharynx window of opportunity cancer chemoprevention study of ACTOplus met® XR (pioglitazone 30 mg and metformin extended release

1000 mg) daily for 10-21 days in subjects undergoing planned surgery or definitive radio/chemotherapy. The study population consists of newly diagnosed subjects  $\geq 18$  years of age with biopsy proven, stage I-IV squamous cell carcinoma, or squamous cell carcinoma in situ of the oral cavity or oropharynx who will be undergoing surgical, radiation or combined modality treatment.

The primary endpoint of the study is the absolute change in proliferation index (Ki67) expression in oral cavity cancer cells from baseline to post-exposure. We will evaluate the difference between the treated and control arms in absolute change in Ki67 using two-sample Student's t-test or Wilcoxon rank-sum test, as appropriate.

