### 13.2 Randomization/Stratification:

Subjects will be randomized in a 2:1 ratio between ACTOplus met® XR and placebo using permuted blocks of size 3. Each block will have a random permutation of two subjects with ACTOplus met® XR and one with placebo. To facilitate timely dispensing of the study agent, each site will receive a block of 3 bottles of study agent upon receipt of drug shipment authorization. When the site has dispensed their last kit from the block of 3, another block of three bottles will be sent until the site has reached the accrual limit assigned in their sub-award. If a site cannot complete a block in accordance with the accrual goals for the study, the site's sub-award will be amended and their remaining accrual slots will be transferred to another site. To preserve the permutation, the site must continue to make every effort to complete a block once they have received it. Due to the small sample size, there will be no stratification analysis per site.

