### 13.3 Accrual and Feasibility:

The sample size for each arm is based on comparing the absolute change in Ki67 between the ACTOplus met® XR arm and the placebo arm. The goal will be to bring to study completion a total of 36 subjects, or 24 subjects in the ACTOplus met® XR arm and 12 subjects in the placebo arm. Since our sample size is fixed at  $N=36$ , and we are randomizing at a ratio of 2:1 between ACTOplus met® XR and Placebo, our sample size/arm for the purpose of power calculations (if we had even sample sizes) would be  $n = 1/\{[1/n_E+1/n_C]/2\} = 16$ . For the power calculation,  $n = [(z_{1-\alpha/2}+Z_\beta)^2 2\sigma^2]/\Delta^2$ .

The table below shows detectable effect sizes (defined as the mean difference in the change divided by the standard deviation of the change) for various significance level  $\alpha$  and power  $1-\beta$  combinations for the primary endpoint. Based on the literature, a mean difference in the change of around 30-40% and a standard deviation of 20-30% may be reasonable to expect [61]. Given those estimates, and the sample size of 36, the minimum effect size we would expect would be at least 1.00; we would be able to detect the effect size of 1.00-1.15 with power 0.80-0.90 for a two-sided level 0.05 Student's t-test.

$\alpha \setminus 1-\beta$	0.80	0.85	0.90
0.05	1.00	1.06	1.15
0.10	0.88	0.95	1.04

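### The primary test of Ki-67 change adjusts for neither baseline Ki-67 nor site; an ANCOVA on the same 36 patients would usually be more precise

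*Combined protocol and SAP*

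**What the plan says.** Section 13.4 defines the endpoint: "The primary endpoint of the study is the absolute change in proliferation index (Ki67) expression in oral cavity cancer cells from baseline to post-exposure". The same section sets the analysis: "The primary analysis will compare the difference in absolute change in Ki-67 between the ACTOplus met® XR and placebo arms", by a two-sided two-sample Student's t-test or "Wilcoxon rank-sum test, as appropriate, at a significance level of 0.05". Section 13.1 agrees: "We will evaluate the difference between the treated and control arms in absolute change in Ki67". Neither section names a covariate, and no adjusted model appears as a sensitivity analysis.

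On allocation, section 13.2 sets 2:1 randomisation in permuted blocks of 3, with each site receiving its own blocks. Section 6.8.2 says "the CLO coordinator will assign the next randomization (bottle) number in sequence for that site". Section 13.2 ends: "Due to the small sample size, there will be no stratification analysis per site".

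Section 13.3 fixes the completed sample at 36 (24 active, 12 placebo). It defines effect size as the difference in mean change divided by the SD of change, and says "we would be able to detect the effect size of 1.00-1.15 with power 0.80-0.90" for a two-sided 0.05 t-test. The number of sites is not stated in section 3 but can be inferred from "an accrual rate of 1-2 participants per month (0.5-1 per site", which implies about two.

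**The concern.** A change score uses the baseline value with its coefficient fixed at 1. Where the true slope of post-treatment on baseline Ki-67 is lower, the change score keeps baseline noise that a regression would remove. A slope below 1 is plausible here, though the documents give no figure for it. Under section 7.6.1, baseline tumour Ki-67 is read from half of a 4 mm biopsy, while for surgical patients the end-of-study tumour tissue comes from the resection specimen. Sampling noise and a change of specimen type both lower the pre/post correlation.

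Bottles are assigned in sequence within site, so allocation is in effect stratified by site. If mean change differs between sites, an unadjusted test leaves that variation in its error term and becomes conservative.

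At stake is precision in a trial that cannot grow. N is fixed, and power at the planned effect is only about 0.80 by the plan's own formula. The analysis model is one of the few things still open, and the data it needs are already collected.

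**Working it through.** **Inputs.** From section 13.3: 24 and 12 patients, two-sided 0.05, effect size in SD-of-change units. Assumed: pre/post correlation ρ from 0.3 to 0.9; post/baseline SD ratio λ = 1 unless stated; two sites of 18.

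**1. The plan's figures.** The equivalent n per arm is 1/{[1/24 + 1/12]/2} = 16. The detectable effect is (z₀.₉₇₅ + z_power)·√(2/16), which gives 0.991, 1.059 and 1.146 at 80%, 85% and 90% power. The plan states 1.00, 1.06 and 1.15, so its table reproduces. For the t-test it names, the standard error at 24/12 is √(1/24 + 1/12) = 0.354 SD. The noncentral t with 34 df then gives power of 0.785 at an effect of 1.00.

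**2. Baseline adjustment.** With equal SDs, the variance of change is 2σ²(1 − ρ) and the residual variance given baseline is σ²(1 − ρ²). Their ratio is (1 + ρ)/2. The ANCOVA with baseline and one site term has 32 df. Estimating the slope inflates the variance by 1 + 1/31. Simulation used 40,000 trials per cell. Effect 1.00:

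| ρ | variance ratio | SE ratio | power, formula | power, simulated | HC3, simulated | mean 95% CI half-width (SD of change) |
|---|---|---|---|---|---|---|
| 0.3 | 0.65 | 0.82 | 0.917 | 0.917 | 0.890 | 0.59 |
| 0.5 | 0.75 | 0.88 | 0.876 | 0.878 | 0.844 | 0.63 |
| 0.7 | 0.85 | 0.94 | 0.833 | 0.834 | 0.794 | 0.67 |
| 0.8 | 0.90 | 0.96 | 0.812 | 0.815 | 0.773 | 0.69 |
| 0.9 | 0.95 | 0.99 | 0.791 | 0.792 | 0.749 | 0.71 |
| t-test | 1 | 1 | 0.785 | 0.784–0.789 | – | 0.71 |

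Null rejection was 0.049–0.051 for the t-test, 0.050–0.051 for ANCOVA and 0.040–0.042 for HC3.

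**3. Where it does not help.** In general the variance ratio is λ²(1 − ρ²)/(1 + λ² − 2ρλ), and the slope is ρλ. With λ = 1.3 and ρ = 0.7 the slope is 0.91 and the ratio is 0.991, or 1.023 after the 1/31 inflation. Simulated power (20,000 trials) is 0.774 for ANCOVA and 0.784 for the t-test. With a slope of exactly 1 and no site effect, the formula gives 0.770.

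**4. Larger effects, ρ = 0.5, t-test against ANCOVA.** Effect 1.15: 0.885 against 0.948. Effect 1.33: 0.955 against 0.986. Effect 1.5: 0.985 against 0.997. The SE ratio stays at 0.88.

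**5. Site, ρ = 0.5.** With no site effect, one to three site terms leave ANCOVA power at 0.877 to 0.875. If two equal sites differ in mean change by 0.5 or 1.0 SD of change (assumed), the t-test has power of 0.764 or 0.707 and null rejection of 0.041 or 0.030. ANCOVA has power of 0.876 or 0.877 and null rejection of 0.048 or 0.050.

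**6. Unequal variances.** With placebo residual SD 1.5 times active, null rejection is 0.077–0.085 for the t-test, 0.084–0.087 for ordinary ANCOVA, 0.051–0.052 for Welch and 0.046–0.047 for HC3 ANCOVA.

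**The case against.** The plan contains no error on this point. Its test is valid, its detectable effects reproduce, and endpoint, test and sizing agree. A simple two-sample test is a defensible choice in a 36-patient study that section 13.5 calls exploratory. That stands, and it makes this an efficiency point.

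The gain cannot be fixed from the documents. It runs from about 13 points at ρ = 0.3 to almost nothing at 0.9, and turns slightly negative when the slope nears 1. Section 13.3 expects a difference of 30–40% with an SD of 20–30%, so effects from 30/30 = 1.0 to 40/20 = 2.0. By an effect of 1.33 the power gain at ρ = 0.5 is about 3 points. This also stands, although the interval remains narrower at every effect size.

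The site part is weaker than the baseline part. Section 13.2 gives small sample size as its reason, and its sentence could mean only that there will be no site-by-site subgroup analysis. Ki-67 is stained and read at one institution, and subtraction removes constant site shifts, so a site difference in mean change is an assumption. But one to three site terms cost almost no power, so small numbers are a weak reason to omit them. Under the subgroup reading, a site covariate does not conflict with section 13.2 at all. Unequal sites (24/9/3) keep the gain: 0.875 against 0.785 at ρ = 0.5.

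Ordinary ANCOVA is no more robust to unequal variances than the planned t-test. HC3 restores error control but has less power than the planned test from ρ of about 0.8. This is why HC3 belongs among the sensitivity analyses.

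**Conclusion.** The concern holds, as a recommended improvement and not as the repair of an invalid test. With equal pre and post SDs, ANCOVA with baseline and site gains about 5 to 13 points of power at an effect of 1.00 for ρ of 0.7 or below, about 3 points at 0.8, and almost nothing at 0.9. The mean CI half-width falls from 0.71 to 0.59–0.67 SD of change for ρ of 0.3 to 0.7. The downside is about 1 point of power when the slope is close to 1. Most of the gain comes from baseline; any gain from site depends on between-site differences that the documents do not give. These sizes rest on assumed correlations, normal data and ordinary standard errors, and are not claimed for HC3. Confidence is medium because the correlation and the SD ratio are unknown.

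**What to change.** In section 13.4, with matching text in 13.1, make the single primary test a two-sided 0.05 ANCOVA of Ki-67 change on arm, baseline Ki-67 and site, with ordinary standard errors. Using post-treatment Ki-67 as the outcome gives the same treatment coefficient. Report the adjusted difference with its 95% CI. Amend the last sentence of 13.2 so that site is a main-effect term in the model, with no analysis by site. Keep the Welch t-test, the rank-sum test and an HC3 version of the ANCOVA as sensitivity analyses; Welch and HC3 cover unequal variances between arms. Make the change before treatment assignments are unblinded.

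The cost is SAP wording and no new data. The model spends 1 df on baseline and 1 df on site if there are two sites, plus 1 df for each further site.
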